1 ABBREVIATIONS USED IN THE PROTOCOL

Abbreviation	Term
AE	Adverse event
BI	Behavioral Intervention
BMI	Body Mass Index
CNWM	Center for Nutrition and Weight Management
EES	Emotional Eating Scale
EMR	Electronic medical record
GHS	Geisinger Health System
GIRB	Geisinger IRB
HIPAA	Health Insurance Portability and Accountability Act
HRQoL	Health-Related Quality of Life
IRB	Institutional Review Board
LOCES	Loss of Control Over Eating Scale
MOS	Medical Outcomes Study
NIH	National Institute of Health
PAI	Physical activity index
PHI	Personal health information
PHQ	Patient Health Questionnaire
PI	Principle Investigator
PPAQ	Paffenbarger Physical Activity Questionnaire
QoL	Quality of Life
RYGB	Roux-en-Y gastric bypass
SAE	Serious adverse event
SAS-SR	Social Adjustment Scale
SD	Standard deviation
SF-36	Short Form Health Survey
STAI	State-Trait Anxiety Inventory
UC	Usual Care
WEL	Weight Efficacy Life-Style

2 ABSTRACT

Rationale: Bariatric surgery patients may experience significant psychosocial changes after surgery, but little psychological support is available beyond support groups postoperatively. Psychosocial changes after surgery, including mood fluctuations, interpersonal issues and substance use, have the potential to lower quality of life and interfere with adherence to the postoperative diet and lifestyle, diminishing weight loss outcomes.

Objective: We will evaluate the effect of a postoperative support program targeting quality of life, psychosocial functioning and adherence to behavior change in Geisinger Health System (GHS) bariatric surgery patients.

Design and Methods: This prospective, randomized pilot trial will evaluate a comprehensive postoperative behavioral support intervention using a 4-month bi-weekly program (BI group) in 40 bariatric surgery patients (all procedure types) from the GHS Center for Nutrition and Weight Management (CNWM), compared to 40 usual care (UC) patients that completed bariatric surgery within one year. The primary outcome will be the difference in quality of life (as measured by the Short Form-36) between groups, as well as differences in psychosocial functioning (mood, eating behaviors) and adherence (diet, physical activity, appointments). Secondary outcomes will include patient satisfaction, treatment feasibility and attrition. Outcomes will be assessed at baseline and treatment completion (4 months). The intervention (BI group) will focus on addressing psychosocial changes after surgery, strategies for postoperative diet and adherence, and preventing weight regain. Patients will collaboratively set goals for diet, physical activity, adherence and other behavioral changes tailored to the needs of each participant. Intervention patients will attend 8, one-hour bi-weekly treatment sessions in a 4-month time period.

Significance: Knowledge gained will help to fill the gaps in understanding regarding the psychosocial benefits of enhanced behavioral support following bariatric surgery, as well as to improve the quality of patient care at GHS and address the obesity epidemic by providing patients the best possible opportunity for long-term weight loss success.

3 BACKGROUND AND SIGNIFICANCE

Bariatric surgery is the most effective long-term treatment for obesity¹, but weight-loss trajectories after surgery vary greatly². Bariatric surgery requires adherence to a highly regimented, lifelong postoperative diet and lifestyle to achieve and maintain optimal weight loss³. However, numerous behavioral and psychosocial factors^{4,5} may contribute to difficulties with compliance, contribute to weight regain, and jeopardize the long-term success of these procedures. While most bariatric surgery programs and third-party payers require psychological evaluations^{3,6} before surgery to identify psychosocial and behavioral factors that may contraindicate surgery³ or be associated with suboptimal weight losses⁴, little psychological support beyond support groups is provided after surgery to help patients adjust to the significant psychosocial changes that may occur after surgery, including the possibility of substance use problems⁷, marital or relationship changes⁸, fluctuations in mood⁸ and even suicidality⁹, or to support the patient to implement and sustain the behavioral changes necessary for postoperative weight loss success³.

Our ability to predict which patients may struggle with weight or psychosocial concerns postoperatively is limited. More than two-thirds^{4,5} of bariatric surgery patients have experienced at least one lifetime mental disorder. Further, a subgroup of patients without known or reported pre-surgical mental health issues experience some degree of psychosocial or behavioral concerns following surgery, which in turn may impact weight and functional outcomes. In a recent survey of more than 150 bariatric surgery patients in Pennsylvania¹⁰, patients reported concerns about their eating behaviors and expressed interest in participating in postoperative programs targeted the prevention of weight regain.

Bariatric surgery patients are expected to lose 30-40% of their initial total body weight, depending on surgery type^{1,11}. Courcoulas et al.² identified five distinct weight loss trajectories among patients who have undergone Roux-en-Y gastric bypass (RYGB), suggesting significant variability in weight-loss results. In this investigation, greater than 20% of patients initiate weight regain one year after RYGB and virtually all patients regain some weight after two years². Adams et al.¹² found that at six years after surgery, only 76% of RYGB patients maintain

greater than 20% weight loss¹² and almost all regained up to 10% of their weight. The etiology of this 10% regain is unclear and may be physiological as much as psychosocial or behavioral. Modifiable psychosocial risk factors, including depression⁴, binge eating behaviors¹³, poor social support⁵ and high life stress⁵, likely contribute to difficulties with postoperative compliance, and in turn, poorer weight outcomes. Psychiatric disorders are associated with general medical non-compliance^{14,15} and they may play a role in difficulties with postoperative compliance. Several studies indicate^{5,16,17} that psychiatric co-morbidity, including depression and anxiety, may relate to postoperative weight loss, but other studies do not find strong associations¹⁸. Sarwer and colleagues¹⁹ found psychiatric medication use to be higher in bariatric surgery patients than the general population. Disordered eating is also common among candidates for bariatric surgery²⁰ and likely contributes to suboptimal outcomes or weight regain postoperatively.

A recent meta-analysis²¹ evaluated the efficacy of behavioral support programs after bariatric surgery on postoperative weight loss. In the studies included, behavioral treatment resulted in greater weight loss compared usual care or no treatment. Patients who received behavioral lifestyle interventions also showed lower levels of maladaptive eating patterns, higher levels of physical activity, better postoperative psychosocial functioning, and greater adherence to postoperative dietary recommendations than controls; however this meta-analysis²¹ identified several areas for future study, particularly the need to study the impact of these programs on more aspects of psychosocial functioning (e.g. quality of life, interpersonal relationships, self-efficacy/esteem), psychopathology (e.g. depression, anxiety, eating disturbances) and physical activity after surgery.

Obesity is associated with diminished quality of life (QoL)²² and QoL²³ is frequently cited as a primary reason that patients pursue bariatric surgery. Evaluating QoL emphasizes patient experience and perception and provides a measurement of treatment efficacy beyond weight loss. In this application, we propose to evaluate the effect of an innovative postoperative support program targeting quality of life, psychosocial functioning and adherence to behavior change in Geisinger Health System (GHS) bariatric surgery patients.

4 HYPOTHESIS AND SPECIFIC AIMS

The objective of this randomized controlled trial is to evaluate the efficacy and feasibility of a 4-month postoperative behavioral intervention (BI) program on psychosocial functioning and compliance in 40 bariatric surgery patients compared to a control group undergoing usual care (UC, n=40).

Knowledge gained will help to 1) fill the gaps in understanding regarding the psychosocial benefits of enhanced behavioral support following bariatric surgery; 2) improve the quality of patient care at GHS and beyond; and 3) address the U.S. obesity epidemic by providing bariatric surgery patients the best possible opportunity for long-term weight loss success. Data will be used for future NIH grant applications (R21, R01) needed to evaluate this program in larger and more diverse cohorts, as well as for manuscript development.

4.1 Hypothesis

We hypothesize that BI patients will experience significant improvements in psychosocial functioning and better compliance compared to UC. As secondary outcomes, we will evaluate within group changes (BI group) from enrollment to completion of 4-month intervention program as well as outcomes in higher risk versus lower risk patients based on their initial preoperative psychosocial evaluations. We hypothesize that the BI group will display higher levels of dietary adherence and physical activity and attend more postoperative appointments, compared to UC.

4.2 Specific Aim 1

To assess the efficacy of a 4-month behavioral intervention (BI) program after bariatric surgery on psychosocial functioning compared to usual care (UC). Psychosocial outcomes assessed will be quality of life (primary), mood (depression/anxiety), eating behaviors, self-efficacy and interpersonal functioning using standardized measures.

4.3 Specific Aim 2

To evaluate the efficacy of a 4-month behavioral intervention program on postoperative dietary and lifestyle adherence compared to the UC.

4.4 Specific Aim 3

To assess the feasibility of a 4-month behavioral program in postoperative bariatric surgery patients. We will evaluate recruitment, attrition, safety and patient/provider satisfaction in the BI group.

5 PRELIMINARY DATA

Modifiable psychosocial risk factors, including mood disorders⁴, likely contribute to difficulties with postoperative compliance as psychiatric disorders are associated with general medical non-compliance^{14,15}. In the GHS bariatric surgery research database (N=3,695), 43% (n=1,580) have at least one psychiatric diagnosis before surgery (ICD-10) and 56% (n=2,045) took at least one psychiatric medication (Table 1). While the rates of psychiatric disorders in bariatric surgery patients are high, particularly depression and anxiety, few programs provide psychological support for patients after surgery beyond monthly support groups.

Table 1: Select psychiatric diagnoses from the EMR in GHS bariatric patients before surgery (N=3,695)

Depression (311)	1,005	27.20%
Anxiety (300)	317	8.60%
Non-dependent Drug Abuse (305)	226	6.10%
Episodic Mood Disorder (296)	196	5.40%
Adjustment Reaction (309)	145	3.90%
Personality Disorders (301)	23	<1.0%
SSRI/serotonin modulators	1,574	42.60%
SNRI	517	14.00%
Misc. Antidepressant	346	9.50%
Tricyclic Agents	267	7.20%
Benzodiazepines	121	3.30%

At GHS, patients considering bariatric surgery undergo preoperative psychological evaluations to evaluate their readiness for surgery. All patients are then given a “traffic light” status (red, yellow, or green) according to their readiness. Patients given a “green” light are cleared for surgery, while “yellow” light patients (~25%) have preoperative milestones that require further attention before surgery (i.e., preoperative weight gain, psychiatric issues that require collateral information or referrals to mental health treatment, and difficulty adopting dietary changes before surgery). We believe that the proposed intervention may be particularly effective in patients that initially received a yellow light, but we will include both initial green and yellow light patients for this pilot study and then evaluate outcomes by light status as a secondary analysis

6 STUDY DESIGN

6.1 Description

This prospective, randomized pilot trial will evaluate a comprehensive postoperative behavioral support intervention using a 4-month bi-weekly program (BI group) in 40 bariatric surgery patients (all surgical procedure types) from the GHS Center for Nutrition and Weight Management (CNWM) compared to 40 usual care (UC) patients. Participants will be randomized to BI or UC using a computer program. Treatment will occur in two session periods to accommodate patients who complete surgery during the study duration.

We will recruit preoperative bariatric surgery patients who are close to their surgery date as well as those who completed bariatric surgery within 18 months. Participants will not be consented until surgery completion. Patients will be recruited via U.S. mail, as well as at support groups/classes and clinic appointments. We anticipate that of the ~25 surgeries conducted monthly, recruitment will take approximately 6 months to recruit 80 patients on a rolling basis. We will run two, possibly three, biweekly groups simultaneously if needed to accommodate patients available for day or evening groups. The primary outcome will be the difference in quality of life postoperatively, between groups, as well as differences in psychosocial functioning (mood, eating behaviors) and adherence (diet, physical activity, appointments). Outcomes will be assessed at time of enrollment and then at after completion of 8 treatment sessions (BI group). Final outcomes assessments will be distributed to BI and UC patients at the same time to maintain consistent data collection intervals between the groups. Secondary outcomes will include patient satisfaction.

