6.2.2 Inclusion Criteria

- Age 18-65 years
- BMI \geq 35 kg/m² at time of surgery

- Primary bariatric surgery completion \leq 18 months
- Understanding of informed consent

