6.3 Recruitment

All bariatric surgery candidates that have been cleared by psychology for surgery (~4-6 weeks before surgery), as well as those who completed bariatric surgery but are less than or equal to 18 months post-surgery, will be informed of the study either via mailed letters (see Attached Recruitment Letter), at support groups/classes or at individual pre or postoperative appointments by study staff.

Mailings will be the primary method of recruitment for patients that have completed bariatric surgery within the last 18 months. A list of names, medical record numbers, addresses, phone numbers, and return appointment dates of those who meet the inclusion and exclusion criteria will be pulled by a data analyst. This information will be used for recruitment purposes.

Potentially eligible patients will be called by a member of the study team to discuss the study in more detail, answer any questions, and if interested, a study visit will be scheduled to review the consent form in detail. Patients that agree to participate will then complete the baseline surveys at that time or can take the surveys home to complete and return in a pre-paid envelope. (See Attached Telephone Screening Script/Surveys)

Patients that have not yet completed bariatric surgery will be approached at either a support group/class or at an individual appointment. If they are approached at support group/class, they will be presented the information about the study in a group setting and given a copy of the consent form that can be taken home for consideration. If they are interested in participating, they will be approached to go over the consent form in detail and sign consent at their first post-operative appointment. After the consent is signed and before randomization occurs, the baseline surveys will be completed either in the clinic or they can opt to take the surveys home to complete and return in a pre-paid envelope.

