6.8.1 Statistical Analysis Plan

Randomization will be conducted using randomization schema generated by the Biostatistician. Randomization to UC or BI will occur following consent. It is plausible that yellow light patients may experience greater benefit from the intervention. We will examine the comparability of demographics characteristics between two groups at baseline. If baseline demographic factors are not balanced between the two groups, we will then adjust for these factors during final analyses.

The primary outcomes will be the difference in mean HRQoL scores (emotional scale) as assessed by the SF-36 between the BI and UC groups at postoperative month 4 (assessment time frame will be postoperative month 1 to month 4). Continuous variables will be analyzed using independent t-tests. We will evaluate the appropriate assumptions using Shapiro–Wilk or Kolmogorov–Smirnov tests (normality) and a Brown–Forsythe test or a Q–Q plot (homogeneity of variance). Should the normality assumption be violated, we will then attempt transformations. If necessary, ANCOVA will be used to control for wave (1 vs 2) or other baseline covariates.

Secondary outcomes include differences between groups in the remaining HRQoL scales. Similar methods as described for the primary outcome will be used for the secondary outcomes. Additionally, within group analyses (secondary) will use paired t-tests. Categorical variables will be analyzed by chi-squared tests.

We will conduct intent-to-treat analysis to determine differences in primary and secondary outcomes using data from all randomized participants. Missing data will be handled using multiple imputation⁵⁵. We will also conduct sensitivity analyses such as best and worst case analyses⁵⁶.

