8.2 Protection of Human Subjects Against Risks

All studies with identifiable data carry the risk of the potential loss of privacy.

We will address this issue in several ways. First, all PHI will be stored on a secure, password protected network to which only limited number of research staff will have access. For data analysis, all data will be de-identified to the extent possible. Any information made available to other investigators will be in a HIPAA compliant format. PHI taken from the medical record will include name, medical record number, address, date of birth, date and type of surgery, appointment attendance, gender, race/ethnicity, weight, height, medications and medical conditions.

We believe that this study poses a low risk to participants; however, should any participant express significant psychiatric distress in group, including but not limited to suicidal or homicidal thoughts, the group leader (a clinical psychology resident) will assess the participant immediately after group and consult with the study PIs ([name] or [name]). The group leader and study PI(s) will refer the participant for further treatment as appropriate. The group leader may also ask disruptive participants to leave group at any time.

Should a participant report post-operative complications following bariatric surgery, the patient will be referred by group leaders or the study PI to the emergency room or to the bariatric surgery clinic, as appropriate.

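### Patients enter anywhere from the first post-operative visit to 18 months after surgery, but time since surgery is neither a named randomisation stratum nor a pre-specified covariate in the primary comparison

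*Combined protocol and SAP*

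**What the plan says.** **Who enters, and when.** Section 6.1 (Description) combines two streams: "We will recruit preoperative bariatric surgery patients who are close to their surgery date as well as those who completed bariatric surgery within 18 months". Section 6.2.2 sets the upper limit as "Primary bariatric surgery completion \leq 18 months". The lower limit follows from section 6.3 (Recruitment): for patients first approached before surgery, "they will be approached to go over the consent form in detail and sign consent at their first post-operative appointment". The abstract gives a different window for the comparator: "compared to 40 usual care (UC) patients that completed bariatric surgery within one year".

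**How they are allocated.** Section 6.8.1 says "Randomization will be conducted using randomization schema generated by the Biostatistician", and sections 6.1 and 6.5 refer to a computer program. None of these places names a stratum, block or minimisation factor.

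**How they are compared.** Section 6.8.1 uses independent t-tests for continuous outcomes, including the primary SF-36 comparison. Two sentences deal with covariates. The first is triggered by observed imbalance and is limited to demographics: "If baseline demographic factors are not balanced between the two groups, we will then adjust for these factors during final analyses". The second allows ANCOVA where it is judged necessary, for wave or for further baseline covariates that it does not name.

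**What is available.** The list of record data in section 8.2 includes "date and type of surgery, appointment attendance, gender", so months since surgery can be derived for everyone. The baseline SF-36 is completed before randomisation (section 6.3).

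**When the outcome is measured.** Sections 6.8.1 and 6.8.2 place it four months after surgery. Section 6.1 and the Measures text in section 6.5 place it at the end of the eight-session period, which is counted from enrolment.

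**The concern.** A patient a few weeks after surgery and a patient 17 months after surgery may be at different points of recovery. If quality of life depends on that stage, an arm that by chance holds more early patients will have a different final mean whatever the programme does. With 40 per arm such imbalance is not rare. The plan commits to no step that would limit it at allocation or remove it at analysis.

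Two things are at stake. One is the estimate from this particular randomisation, which section 4 intends for use in grant applications for larger studies. The other is precision: variance that a known baseline variable could explain stays in the error term. The optional ANCOVA does not settle either, because choosing covariates after seeing the data is the discretion that an analysis plan should remove.

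**Working it through.** **1. The plan's own figures (section 6.8.2).** With 40 per group, a 2/3 SD difference and two-sided alpha of 0.05, the noncentral t gives 83.8% power (normal approximation 84.6%). The plan states 83%, so this reproduces. The confidence-interval half-width also reproduces: 1.96 × 10.1 × √(2/40) = 4.43, stated as 4.4.

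**2. What the documents give on effect size.** The table in section 6.8.2 gives, before and after surgery:
- Role-Emotional 74.9 (SD 34.4) and 92.3 (SD 22.1), a change of 17.4.
- Mental health composite 48.9 (SD 10.1) and 52.1 (SD 8.4), a change of 3.2.

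These compare pre-operative with post-operative patients. No participant is pre-operative at either assessment. Below, the changes serve only as an assumed ceiling for the early-late gap.

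**3. How often imbalance arises.** Assume 40 of the 80 patients are early and 40 late.
- SD of the between-arm difference in proportion early: √(2 × 0.25/40) = 0.112.
- Probability of a 24/16 split or worse, in either direction (hypergeometric): 0.117.

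**4. Shift from a 24/16 split.** The arms hold 60% and 40% early patients, a difference of 0.20. Shift = 0.20 × gap.

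| Scale | Gap | Shift | SD used | 2/3 SD target | Shift/target | SE = SD × √(2/40) | Shift/SE |
|---|---|---|---|---|---|---|---|
| Role-Emotional | 17.4 | 3.48 | 22.1 | 14.7 | 24% | 4.9 | 0.70 |
| Role-Emotional | 17.4 | 3.48 | 34.4 | 22.9 | 15% | 7.7 | 0.45 |
| Composite | 3.2 | 0.64 | 8.4 | 5.6 | 11% | 1.9 | 0.34 |
| Composite | 3.2 | 0.64 | 10.1 | 6.7 | 10% | 2.3 | 0.28 |

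Halving the gap halves each shift. A more uneven split enlarges it in proportion.

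**5. Precision.** Variance explained by an early/late factor is R² = 0.25 × gap² / (SD² + 0.25 × gap²). Power after adjustment uses the effect (2/3)/√(1 − R²).
- Role-Emotional, SD 22.1: 75.7/(488.4 + 75.7) = 0.134; power 88.6%.
- Composite, SD 8.4: 2.56/(70.56 + 2.56) = 0.035; power 85.0%.
- Unadjusted: 83.8%.

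**6. A second route, without the table.** Let r be the assumed correlation between time since surgery and the outcome, from 0.1 to 0.5. The 95% limit of chance imbalance is 1.96 × √(2/40) = 0.44 SD of time since surgery. This is about 2.2 months if entry is uniform over 0.5 to 18 months (SD 17.5/√12 = 5.05; also assumed). The shift at that limit is r × 0.44, which is 0.04 SD (r = 0.1), 0.13 SD (r = 0.3) or 0.22 SD (r = 0.5): 7%, 20% or 33% of the target. Type I error conditional on that imbalance is 5.3%, 7.9% or 12.9%.

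**7. Validity on average.** In 20,000 simulated trials with r = 0.4, the unadjusted t-test rejected a true null in 5.1%.

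**8. Timing.** A patient who enrols 17 months after surgery and is assessed about four months later is at about month 21. That cannot be post-operative month 4.

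**The case against.** The strongest reply is that the documents do not show that recovery stage matters for this outcome within the window. The table in section 6.8.2 has no series of post-operative time points. The background remark that "greater than 20% of patients initiate weight regain one year after RYGB" concerns weight, not SF-36, and a minority of patients. The comparison also uses the final score, when even the newest patients are some four months further on. All of this stands, and it makes the shift in points a ceiling under assumption.

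Chance imbalance is also already covered by the t-test's error rate. That is correct unconditionally. It does not restore lost precision, and it does not help once a particular allocation is known to be uneven.

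The optional ANCOVA would permit adjustment for time since surgery. Wave may be a partial proxy, since the second session period exists partly for patients operated on during the study. Both points stand, so the gap is one of pre-specification. Wave remains weak, because patients at any stage can enter either wave. Silence on strata may mean only that the schema's details are unreported.

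If section 6.8.1 were read literally, with everyone assessed at post-operative month 4, recovery stage would be nearly fixed and the point would largely fall away. Sections 6.1, 6.2.2 and 6.3 do not allow that reading.

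A reader might go further and infer that the comparison is biased, or that early patients are improving while late ones are flat or declining. The documents support neither. Randomisation prevents bias on average, and no such courses are reported.

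**Conclusion.** The point holds as one of conditional imbalance and lost precision, not of bias or inflated overall error. Entry spans the first post-operative visit to 18 months, the primary test is unadjusted, and time since surgery has no pre-specified role although the surgery date is collected.

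The size is not known from the documents. With half the patients early and the early-late gap as large as the pre-to-post change, a 24/16 split shifts Role-Emotional by 3.5 points (15–24% of the target, depending on the SD) or the composite by 0.64 points (about 10–11%). Splits that uneven or worse have probability 12%. Under the same assumptions adjustment brings power to about 85–89%. A smaller gap reduces all of these. The change is still worth making because it costs almost nothing.

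Separately, and without any assumption, the stated outcome timing and the abstract's one-year window conflict with the 18-month entry window and the assessments counted from enrolment.

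**What to change.** - **Analysis (section 6.8.1).** Make the primary and secondary between-group comparisons of continuous outcomes an ANCOVA with the baseline score and time since surgery at randomisation, whether or not imbalance is seen. Derive time since surgery from the recorded surgery date. Enter it in categories or in a form that allows a non-linear relation, since a single straight line may not fit a recovery course.
- **Allocation.** If allocation has not begun, stratify the schema by two levels of time since surgery, for example newly operated patients versus those recruited later by mail, or a month cut-off. State the factor in the plan.
- **Wording.** Reconcile the outcome timing in sections 6.8.1 and 6.8.2, and the one-year window in the abstract, with the 18-month criterion and the assessment schedule in sections 6.1 and 6.5.

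**Cost.** One or two degrees of freedom for time since surgery and one for the baseline score, a slightly more complex allocation, and edits to the text. No new data and no additional patients are needed.
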